#### **Skin Biopsies:**

Biopsies will be obtained to examine the effects on the skin following radiofrequency treatment. Sections of skin will be removed using the punch biopsy technique to render a microscopic

diagnosis. Each specimen will first be preserved with a fixative and then stained using Hemotoxylin & Eosin, Verhoeff and Masson Red/Fast Green or nitroblue tetrazolium chloride (NBTC) staining methods. If using Hemotoxylin & Eosin, Verhoeff and Masson Red/Fast Green staining, samples will be assessed and evaluated by the amount of collagen and elastin stained. If using NBTC staining, samples will be assessed and evaluated to differentiate between the bluestained viable cells and the unstained thermally damaged cells. A histological analysis will be provided by the Investigator.

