## **1.2 Objectives**

- 1. Primary Objectives:
  - Assessment of safety of the study device through the collection of side effects throughout the study.
  - Assessment of the efficacy of the study device through Investigator and subject satisfaction.
  - Evaluation of baseline photographs compared to post treatment images.
- 2. Assessments:
  - Treatment discomfort evaluation
  - Subject treatment experience questionnaire
  - Clinician ease of use questionnaire
  - Clinician and subject satisfaction questionnaire
  - Treatment area photograph blinded evaluation
  - Baseline and short-term histological tissue response as seen in biopsies.

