#### **2.10 Biopsy Portion of the Study**

- Up to 6 subjects will enroll in the biopsy portion of this study. If the subject has enrolled, the following will also be performed:
  - Biopsies will be taken from the test spot area day of treatment and may be taken 0-24 hours, 25-48 hours, 3-7 days, and 30 days post treatment.
  - Biopsy subjects may receive up to 2 biopsies at each visit, totaling 10 biopsies.
  - A local anesthetic, such as lidocaine, may be injected to the area prior to biopsy.
  - A 2 mm or 3mm punch biopsy (based on Physician assessment) will be taken from the treatment area.
  - Sutures will be uses to close the incision site.
  - The subject will be required to attend a 1 week (7-14 days) post the 7 day biopsy visit and a 1 week (7-14 days) post 30 day biopsy follow up visit to remove the sutures and assess side effects.
- The following post biopsy treatment instructions will be reviewed:
  - Slight redness, initial tenderness to the wound site is normal; however, if you experience more redness, swelling, pain, pus, or drainage contact the study site immediately.
  - If the biopsy site begins to bleed, apply direct pressure for 10-20 minutes. If it continues to bleed, call the study site immediately.
  - Keep the wound dry today and remove bandage in 24 hours and leave off.
  - Avoid hot tubs, pools, and ocean until sutures are removed. Avoid soaking in water until 14 days after your biopsy.
  - When showering, wash carefully and do not scrub or traumatize the treated skin, or allow spray of shower to strike the skin directly. If the skin is treated harshly, this can increase the risk of scarring.
  - After showering, lightly pat dry the wound or let it air dry, then cover the biopsy site with an application of Vaseline (or petroleum jelly) at least 1-2 times daily. Keeping the wound moist reduces infection, minimizes scarring, and prevents crust formation over the wound.
  - Band-Aids (or any generic Adhesive Bandages) may be used for sleeping or in daily routines where the area may be rubbed/irritated. Whenever possible, keep Band-Aid (or generic Adhesive Bandage) off of the area and keep the area moist with Vaseline (or petroleum jelly) as previously described but do not allow drying out and forming a hard scab.

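### Section 2.14 fixes biopsies before a stain read as cell viability, and does not hold the stain panel or the scale of the reading constant across a subject's own time points

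*Combined protocol and SAP*

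**What the plan says.** Section 1.2 lists among the assessments: "Baseline and short-term histological tissue response as seen in biopsies". The biopsy schedule in section 2.13 labels the treatment-visit biopsy as the control and sets four later biopsy time points, the last at 30 days. The intended reading is therefore a comparison with baseline.

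On processing, section 2.14 (Skin Biopsies) says: "Each specimen will first be preserved with a fixative and then stained using Hemotoxylin & Eosin, Verhoeff and Masson Red/Fast Green or nitroblue tetrazolium chloride". The two panels have different readouts:

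- For the Hematoxylin & Eosin, Verhoeff and Masson panel, "samples will be assessed and evaluated by the amount of collagen and elastin stained".
- For NBTC, the purpose is to "differentiate between the bluestained viable cells and the unstained thermally damaged cells".

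On sampling, section 2.10 says: "Up to 6 subjects will enroll in the biopsy portion of this study"; "Biopsy subjects may receive up to 2 biopsies at each visit, totaling 10 biopsies"; and "A 2 mm or 3mm punch biopsy (based on Physician assessment) will be taken from the treatment area".

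The protocol does not name the fixative or describe separate handling for NBTC. It does not say who chooses the panel, at what level the choice is made, or whether the panel or punch size stays the same within a subject. Sections 2.16.2 to 2.16.6 contain no analysis specific to histology.

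**The concern.** There are three separate weaknesses, strongest first.

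1. **Fixation before a viability stain.** The rule covers every specimen without exception. If fixed cells can no longer show viability, an unstained cell may be unstained because of the fixative. The reading that should show heat damage would then be uninterpretable.
2. **Panel not tied to the subject.** One panel measures connective-tissue staining and the other cell survival. A control on one panel and a later sample on the other give no within-subject change.
3. **Unscaled readout with variable punch size.** An amount of stained tissue depends on how much tissue is in view, and the punch diameter may vary.

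Histology is the plan's direct look at what the device does in tissue, and a subject may give up to 10 punch biopsies for it. Section 2.16.1 also sets a success criterion that can be read as covering any assessment. Tissue obtained at that burden should be interpretable.

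**Working it through.** **The plan's own figure.** Section 2.10 allows 2 biopsies per visit, and the section 2.13 schedule has 5 biopsy visits (control, 0-24 hours, 25-48 hours, 3-7 days, 30 days). 2 × 5 = 10 biopsies per subject, which matches the stated total. With up to 6 subjects, the maximum is 6 × 10 = 60 specimens.

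**Fixation.** This is a matter of reading, not arithmetic. Set three statements from section 2.14 side by side: all specimens are fixed and then stained; NBTC is one of the stains; NBTC is read as living versus heat-damaged cells. The missing link, that a fixative ends viability, is general histochemistry and is not in the documents. The size of any effect depends on the unnamed fixative and cannot be computed. A control specimen is fixed too, so it could expose an artefact, but only if it was itself stained with NBTC, which the plan does not require.

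**Panel matching.** The outcome depends on the level at which the panel is chosen, which is not stated. If it is set once per subject, all time points match. As the opposite illustration, assume one biopsy per visit and an independent choice each time, with share p going to the collagen and elastin panel:

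- P(all five time points on one panel) = p^5 + (1 − p)^5
- P(control and day 30 on one panel) = p² + (1 − p)²

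| Assumed p | All five match | Control and day 30 match |
|---|---|---|
| 0.5 | 6.3% | 50% |
| 0.7 | 17.1% | 58% |
| 0.9 | 59.1% | 82% |

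The documents give no p and do not say that choices are independent. The table shows what the wording permits and is not an estimate for this trial.

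**Punch size.** Inputs are the 2 mm and 3 mm diameters in section 2.10.

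- Whole-punch area: π × 1² = 3.14 mm² against π × 1.5² = 7.07 mm²; ratio (3/2)² = 2.25.
- Width of a section cut perpendicular to the skin: 3/2 = 1.5.

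The plane of section is not stated, so an unscaled amount could differ about 1.5-fold to 2.25-fold with no change in the skin. A proportion would largely remove this. It has little bearing on a stained-versus-unstained reading such as NBTC.

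**The case against.** The best case for the plan is that most of this is silence and not error. Much of that stands, and it rules out several stronger readings.

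- **A reader might infer that the stain is chosen specimen by specimen.** The text does not say so. It joins two methods with an or and gives no unit of choice. Appendix A shows NBTC was added on July 31, 2020, after the biopsy portion was added on December 10, 2019, so the or may only separate earlier from later subjects. What remains is that nothing prevents mixing within a subject.
- **A reader might infer that fixation will overstate heat damage at every time point.** The documents do not show this. An NBTC-stained control without stain would reveal the artefact. Section 3.3 describes injury to the dermis that spares the epidermis, so a treated section may also carry its own reference tissue, and a general loss of stain might be noticed. But noticing it would only show that the reading had failed; it would not recover it.
- **A reader might infer that no usable tissue result is left, or that only three subjects will have either readout.** Neither follows. Each specimen still describes its own time point, pairs are lost only if panels are actually mixed, and two specimens at a visit could supply both readouts.
- **A reader might apply the 2.25 ratio to every reading.** It holds only for whole-punch area, and section 2.14 does not say that the amount is an unscaled total.

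It is also fair to say that this is a self-described feasibility study, and that histology covers up to 6 of 120 subjects and is not listed as a primary objective. That limits the impact. It does not remove the stated rule that every specimen is fixed before a viability stain.

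**Conclusion.** The point holds as a real but limited flaw that should be corrected.

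- **Fixation** is the firmest part, because it follows from an explicit rule and not from missing detail. It rests on the laboratory principle that fixed cells are no longer viable, which the laboratory should confirm for the fixative used. The supportable claim is that lack of stain could reflect processing, not that it will.
- **Panel consistency** is an omission. Some control-to-later pairs among at most 6 subjects may be unusable; how many cannot be determined from the documents.
- **Punch size** is the weakest part: about 1.5-fold to 2.25-fold, and only if the collagen and elastin amount is not scaled to the tissue examined.

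The consequences are confined to the descriptive histology assessment. The primary efficacy analysis, CGAIS at 30 days after the last treatment (section 2.16.5), is unaffected.

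**What to change.** Amend section 2.14, with matching wording in section 2.10:

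1. Limit the fixation step to specimens for the Hematoxylin & Eosin, Verhoeff and Masson panel, and have the laboratory specify in writing how NBTC specimens are handled.
2. Assign each biopsy subject in advance to one panel for the control and all later specimens. Where two biopsies are being taken at a visit anyway, one may go to each panel. Do not make the optional second biopsy a requirement for this purpose.
3. Report collagen and elastin as percent stained area relative to the subject's own control. Leave punch size to the physician, as now, and record it for each specimen.

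The cost is protocol and laboratory wording, with no biopsies beyond those that would be taken anyway. The downside is fewer subjects per panel if panels are split between subjects: an even split of 6 leaves 6/2 = 3 on each. Assigning all subjects to one panel avoids this but gives up the other readout.

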## 2.15 Adverse Event Recording

All data captured must be supported by the Investigator's timely assessment and documentation of the adverse event in the case report forms or source documents. All documented adverse events will be reviewed by the Sponsor or designee to determine whether the adverse event meets regulatory reporting requirements and to ensure timely adverse event reporting to meet local and global regulatory requirements. All adverse events must be followed until their resolution.

#### Adverse Events Pertaining to the Potenza™ Device:

- Temporary erythema: area of treatment may turn red right after treatment, but this symptom disappears within 48 hours after treatment
- Temporary tingling: slight edema may occur right after treatment, but this symptom disappears within 48 hours after treatment.
- Burning sensation: patients may feel uncomfortable temporarily while receiving treatment.

Other possible adverse effects may include pain/tenderness, pinpoint bleeding, folliculitis, skin burn, hypopigmentation, hyperpigmentation, infection, paresis, scarring, bruising, acne, dryness, eye twitching, eye tearing, petechiae, skin textural irregularity, and allergic reaction which may be transient and resolve over time.

#### **Adverse Events Pertaining to Neutral Pad:**

Mild heat or hot spots may be felt during treatment by the subject. If the subject reports heat at the pad site, evaluate the site, check for epidermal injury. Skins burns may occur if subject does not report if the pad becomes too hot.

#### Adverse Events Pertaining to Anesthesia:

Topical anesthesia, such as but not limited to; EMLA, LMX and Lidocaine/Tetracaine, or a local anesthetic will be used. The most common side effects for most anesthetics include redness, blanching, swelling and application site reaction.

Less common side effects include; large swellings that look like hives on the skin or in the mouth or throat. Pain, burning, paleness and altered temperature sensation. Subjects may be allergic to the contents of any anesthetic which may cause allergic-type reactions including anaphylactic symptoms and life-threatening or less severe asthmatic episodes in certain susceptible people.

#### **Adverse Events Pertaining to Nitronox:**

May experience nausea, vomiting, excessive sweating, euphoria, excitement, deep sedation, drowsiness, sleep, dizziness, lightheadedness, dysphoria, amnesia, and headaches.

#### Adverse Events Pertaining to the Surgical Marker:

Using surgical marker has minimal risks and may produce effects on the body such as redness or a rash. Markings may remain visible for a few days or may be removed with alcohol.

#### Biopsies

Complication with biopsies can include pain, redness, swelling, infection, bleeding, scarring and skin texture irregularities.

#### **Other Cautions:**

Incomplete response or no response may occur since some subjects may not respond to treatment.

#### 2.16 Statistical Analysis

#### 2.16.1 Hypothesis

For this study to be considered a success, the Investigator and subject satisfaction rates will be  $\geq 80\%$  and if the side effect profile is acceptable to the Physician as it relates to this type of treatment. In cases where the subject's improvement is being graded on a scale, such as the GAIS scale, we will test the statistical significance of our results against a hypothetical population that would have no change (average score of 4).

For secondary objectives to be considered a success, the results from any assessments will need to be statistically significant or have  $\geq 80\%$  response rate.

#### 2.16.2 Sample Size Rationale

Based on the need for the data collected from this study, it was determined that a total of 120 patients would be required for the study, including departures.

#### 2.16.3 Patient Populations

Interim results may be collected and reported. All data will be analyzed at the end of the study. The primary analysis will be performed by the intention-to-treat approach. Everyone who begins the treatment is part of the study whether he or she completes the study or not. Additional perprotocol analysis may also be performed on subjects who complete the entire clinical trial according to the protocol. The most appropriate method of handling missing values will be chosen based on the individual trial goals, endpoints and context.

The analysis of demographic, medical history, and efficacy variables will be based on all patients who are randomized and receive at least one treatment. The analysis of safety data will be based on all patients who are randomized, receive at least one treatment, and have at least some safety data.

#### 2.16.4 Analysis of Demographic and Medical History Variables

Summaries will be prepared for all important demographic and medical history variables. For quantitative variables summaries will include the sample size, mean, median, standard deviation, minimum, and maximum. For these variables the treatment groups will be compared using either a t-test or a Wilcoxon Rank Sum test, as appropriate. For categorical variables the summaries will

include the sample size and the number and percent of patients for each outcome. For these variables the treatment groups will be compared using Fisher's Exact test. Statistical significance will be declared if the two-sided p-value is < 0.05.

#### 2.16.5 Analysis of Efficacy Variables

The primary efficacy variable is the change from baseline to visit 8 (30 days post last treatment) with respect to the treated condition evaluated by physician grading with CGAIS. Baseline is defined as the last assessment prior to the first treatment. The change from baseline to visit 8 will be analyzed using a Mixed Model Repeated Measures Analysis of Variance. A pairwise treatment group comparison at visit 8 will be performed using the results of this analysis. If a patient has no post-baseline assessment of the primary efficacy variable the patient data will be excluded from the statistical analysis of the improvement. Statistical significance with respect to the treatment group comparison at visit 8 will be declared if the two-sided p-value is < 0.05. For each treatment group summaries will be prepared for both the observed assessment and the change from baseline. Subject satisfaction results from Visit 9 will also be included in the summary. The summaries will include the sample size, mean, median, standard deviation, minimum, and maximum. Categorical variables will also include a summary which will include the number and percent of patients for each outcome. The statistical significance of the mean change from baseline for each treatment group will be determined using a student's paired t-test.

The secondary efficacy variables will be determined at a later date based on image grading. As with the primary efficacy variable the assessment at Visit 8 (30 days post last treatment) will be primary. The analysis and summaries for any secondary efficacy variables will be the same as that described for the primary efficacy variable. Statistical significance with respect to the treatment group comparison at visit 8 will be declared if the two-sided p-value is < 0.05.

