#### **Physician Questionnaire:**

The Clinical Global Aesthetic Improvement Scale (CGAIS) ranging from "worse" to "very much improved" will be used to judge the improvement as seen by the treating Investigator.

Global Aesthetic Improvement Scale Assessment				
Rating	Description			
1	Very Much Improved- Optimal cosmetic result in this subject			
2	Much Improved- Marked improvement in appearance form the initial			
2	condition, but not completely optimal for this subject.			
2	Improved- Obvious improvement in appearance from initial condition, but a			
3	re-treatment is indicated.			
4	No Change- The appearance is essentially the same as the original condition.			
5	Worse- The appearance is worse than the original condition.			

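### Section 2.16.5 gives CGAIS a pre-treatment baseline and change-score analysis, but CGAIS already rates change; this conflicts with the test against 4 in 2.16.1

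*Combined protocol and SAP*

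**What the plan says.** Section 2.16.5 (Analysis of Efficacy Variables) opens: "The primary efficacy variable is the change from baseline to visit 8 (30 days post last treatment) with respect to the treated condition", as graded by the physician with CGAIS. It continues: "Baseline is defined as the last assessment prior to the first treatment". Three analyses follow from that definition:

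- a mixed-model repeated-measures analysis of the change, with a pairwise treatment-group comparison at Visit 8 judged at two-sided 0.05;
- descriptive output: "For each treatment group summaries will be prepared for both the observed assessment and the change from baseline";
- a within-group test: "The statistical significance of the mean change from baseline for each treatment group will be determined using a student's paired t-test".

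Patients with no post-baseline assessment are left out of the analysis.

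Section 2.14 (Physician Questionnaire) says that CGAIS "will be used to judge the improvement as seen by the treating Investigator". The scale runs from 1 (very much improved) to 5 (worse), and grade 4 reads: "No Change- The appearance is essentially the same as the original condition".

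Section 2.16.1 (Hypothesis) says that results on a scale such as GAIS will be tested "against a hypothetical population that would have no change (average score of 4").

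**The concern.** A change-from-baseline analysis needs a quantity that can be measured both before and after treatment. CGAIS is not one. The rater compares the subject's appearance now with the appearance before treatment, so the grade is already the change. Before the first treatment there is nothing to compare, and subtracting a pre-treatment grade would take one change from another.

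Section 2.16.5 nevertheless defines baseline as an observed assessment, neither mentions 4 nor refers to 2.16.1, and builds every CGAIS analysis on the difference. Two sections of the same statistical chapter thus give different instructions for the only primary efficacy variable that 2.16.5 names. One points to a one-sample test against a constant, the other to a paired test against an observed value. An analyst has to choose between them. A site following 2.16.5 to the letter might start recording pre-treatment grades that carry no information.

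**Working it through.** **Plan's own figure.** The only planning number is 120 subjects including departures (2.16.2). No effect size, SD, power or dropout rate is given, so it cannot be reproduced. This point does not depend on it.

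**Step 1: is a pre-treatment grade meaningful?** In 2.14, grades 2 to 5 are worded against the initial or original condition. Grade 1 is described as an optimal result for the subject without naming that condition, but its label, very much improved, implies the same comparison. The scale as a whole rates improvement.

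**Step 2: is a pre-treatment grade scheduled?**

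- The 2.13 table marks no clinician questionnaire at Visit 1.
- It does mark clinician questionnaires at Visits 2-6, the treatment visits, without saying which ones.
- Section 2.8 names ease of use as the clinician questionnaire that may be done after treatment.
- Section 2.9 places the physician questionnaire at the follow-up visits.

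No CGAIS grading before first treatment is clearly scheduled. The mark at Visits 2-6 means that one cannot be ruled out entirely.

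**Step 3: what happens if 4 stands in for baseline?** Let y be the Visit 8 grade and d = y - 4. Subtracting a constant moves the mean and leaves the SD alone, so

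t(paired) = mean(d) / (SD(d)/√n) = (mean(y) - 4) / (SD(y)/√n) = t(one-sample against 4).

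As an illustration, assume 120 Visit 8 grades with 6, 24, 54, 30 and 6 subjects at grades 1 to 5. The documents give no distribution.

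- Mean grade = (6×1 + 24×2 + 54×3 + 30×4 + 6×5)/120 = 366/120 = 3.05.
- Sum of squared deviations = 101.7; SD = √(101.7/119) = 0.924.
- Mean change = 3.05 - 4 = -0.95, with the same SD of 0.924.
- t = -0.95/(0.924/√120) = -11.257, whether run as a paired or a one-sample test.

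The equality is algebraic and holds for any distribution of grades. It holds for the repeated-measures model too: replacing y by y - 4 lowers the intercept by 4 and leaves the visit effects and standard errors unchanged.

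**Step 4: does the reference need stating?** Assume a no-effect sample of 15, 90 and 15 subjects at grades 3, 4 and 5 (mean 4.0, SD 0.502, n = 120).

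| Constant used as baseline | Mean change | t |
|---|---|---|
| 3 | +1.0 | 21.8 |
| 4 | 0 | 0 |
| 5 | -1.0 | -21.8 |

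Only 4 gives a correct null. The documents propose no other constant; the table shows only that the analysis depends on a value that 2.16.5 leaves out.

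**Step 5: does the group comparison have two groups?** Section 2.2 describes a prospective, open-label, multi-center study, and the protocol names one device. Section 2.16.3 mentions randomised patients and 2.16.5 mentions treatment groups, but no second group is defined anywhere.

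**The case against.** The strongest reply is that the reference is already in the plan. Section 2.16.1 names the GAIS scale and the value 4, which is also the scale's own no-change grade. On that reading inference is untouched, as Step 3 confirms, and all that is missing is a cross-reference. The opening sentence of 2.16.5 can also be read as saying that the condition changes and CGAIS grades that change, with baseline meaning the state being compared.

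Much of this stands: the plan is workable once 4 is used. It does not remove the point. Section 2.16.5 gives its own definition of baseline as an assessment, asks for the observed value and the change as separate summaries, and prescribes a paired test. Those instructions do not fit a constant reference, so the two sections have to be reconciled.

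A reader might infer more than the documents support:

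- **That the primary variable cannot be computed for any subject.** This goes too far. Section 2.16.1 supplies a reference, and the schedule marks unspecified clinician questionnaires at Visits 2-6.
- **That the fault carries into the 80% satisfaction criterion in 2.16.1.** That section treats satisfaction rates and graded improvement in separate sentences, and 1.2 lists a clinician satisfaction questionnaire. Nothing says that CGAIS supplies the rate.

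The study is also described as a feasibility study (2.1), and its headline success rule is not this p-value. That limits the consequences.

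**Conclusion.** The concern holds as a wrong-as-written rule. For CGAIS, the baseline definition, change summaries and paired t-test in 2.16.5 do not apply, and they conflict with 2.16.1. With 4 as the reference, the t statistic does not change at all and the change summaries add nothing to the observed ones. The treatment-group comparison at Visit 8, and the 0.05 rule attached to it, have no second group to work on.

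The conclusion rests on the scale wording in 2.14 and on the equivalence in Step 3. It does not rest on the assumed grade distributions, which only illustrate it. It should be corrected before data are analysed, but it does not call the collected data into question.

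**What to change.** In 2.16.5:

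1. Define the primary efficacy variable as the CGAIS grade at Visit 8.
2. For CGAIS, delete the baseline definition, the change-from-baseline summaries and the paired t-test.
3. Test the grade against 4, as 2.16.1 already provides. Name the test in advance (for example, one-sample t or signed-rank) and state its significance level, since the present 0.05 rule is tied to the group comparison.
4. If the repeated-measures model is kept, fit it to the post-treatment grades and test the Visit 8 mean against 4, or equivalently fit grade minus 4 and test against 0. Subjects with an earlier post-treatment grade but no Visit 8 grade then stay in, as the present exclusion rule intends; a test on observed Visit 8 grades alone would lose them. State which of the two is the primary analysis.
5. Remove the pairwise treatment-group comparison and its significance rule for CGAIS.

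This is a small wording change that needs no new visits or measurements. The downside is a less elaborate stated analysis.

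### The analysis plan's only p < 0.05 rules for efficacy attach to a treatment-group comparison, but the study defines a single open-label cohort, and the one-group tests it does contain carry no significance level

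*Combined protocol and SAP*

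**What the plan says.** **Design.** Sections 2.1 and 2.2 describe an open-label, multi-centre study of up to 120 subjects at 5 centres, all treated with the same device up to 5 times. Section 2.5 assigns identification numbers in chronological order. The schedule in 2.13 is a single schedule with no allocation step.

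**Analysis sets (2.16.3).** The demographic, medical history, efficacy and safety sets are limited to patients who were randomised and treated. The same section takes an intention-to-treat approach and counts every person who starts treatment.

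**Demographics (2.16.4).** Treatment groups are compared by t-test, Wilcoxon rank sum or Fisher's exact test, at two-sided p < 0.05.

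**Efficacy (2.16.5).** The primary variable is change in CGAIS from baseline to Visit 8, analysed with a mixed model for repeated measures. Then: "A pairwise treatment group comparison at visit 8 will be performed using the results of this analysis". The decision rule reads "Statistical significance with respect to the treatment group comparison at visit 8 will be declared" if two-sided p is below 0.05, and it is repeated for the secondary variables. The section adds "The statistical significance of the mean change from baseline for each treatment group will be determined using a student's paired t-test", and "Baseline is defined as the last assessment prior to the first treatment". On secondary variables it says "The secondary efficacy variables will be determined at a later date based on image grading", with the same analysis as the primary.

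**Hypothesis (2.16.1).** For improvement graded on a scale such as GAIS, "we will test the statistical significance of our results against a hypothetical population that would have no change (average score of 4". Study success is separate: Investigator and subject satisfaction rates of at least 80%, and "if the side effect profile is acceptable to the Physician as it relates to this type of treatment".

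**The concern.** The efficacy text reads as if written for a randomised trial with at least two arms. In a one-cohort study the comparison that carries the significance rule does not exist. The level of 0.05 is therefore attached to nothing that can be computed, while the tests that can be computed have no level.

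At stake is whether the primary efficacy variable has a usable, prespecified criterion for statistical significance. Secondary objectives are also touched, because 2.16.1 lets them succeed by being statistically significant or by a response rate of at least 80%. The gap is best closed in writing before the final analysis: the study is open label, 2.16.3 allows interim results to be reported, and Section 5.0 lets the sponsor ask for data after each visit.

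**Working it through.** **Plan's own figure.** The only sample-size figure is 120 (2.16.2). It comes with no effect size, SD, power or dropout rate, so it cannot be reproduced. The point does not rest on it.

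**Step 1: count the wording in Section 2.16.**
- Randomised status as a condition: 2 times, both in 2.16.3.
- Treatment group or groups: 2 (2.16.4) + 5 (2.16.5) + 1 (2.16.6) = 8 times.
- Statements of two-sided p < 0.05: 1 (2.16.4) + 2 (2.16.5) = 3, all about a group comparison.
- One-group tests: 2 (against 4; paired t-test). Levels stated for them: 0.

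**Step 2: can the comparison be estimated?** With g groups there are g(g − 1)/2 pairwise contrasts; g = 1 gives 0. Equivalently, an intercept plus a group term has rank 1 when everyone is in the same group, so the group effect is not estimable. The mixed model can still give a Visit 8 mean; only the comparison step fails.

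**Step 3: is there a baseline CGAIS?** In 2.14 each CGAIS category is defined relative to the original condition, and 4 means no change. The rating is already a change score. The schedule marks no clinician questionnaire at Visit 1, and the only clinician form that the text names around treatment visits is the ease-of-use form in 2.8, after treatment. The paired t-test therefore needs a baseline fixed at 4, which the plan does not state.

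**Step 4: with baseline fixed at 4, do the two one-group tests differ?** Each paired difference is x − 4, so t = (mean − 4)/(SD/√n) in both. They are the same test.

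**Step 5: how does that test behave at n = 120?** Illustrative data with k patients rated 3 and the rest rated 4:
- k = 3: mean 3.975, SD 0.157, SE 0.157/√120 = 0.0143, t = −0.025/0.0143 = −1.75, p = 0.083.
- k = 4: mean 3.967, SD 0.180, SE 0.0165, t = −0.0333/0.01646 = −2.03, p = 0.045. The 95% CI is 3.967 ± 1.980 × 0.01646, or 3.934 to 3.999.

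Four improved patients out of 120, with none worse, would be enough. The p-value therefore needs the mean and interval beside it. At 80% power and an assumed two-sided 0.05, the detectable shift is 0.258 SD with 120 rated patients and 0.289 SD with 96 (an assumed 20% loss).

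**Step 6: does missing Visit 8 data require the mixed model?** The documents give no inputs, so assume SD 0.75, a correlation ρ of 0.3 to 0.6 between an earlier rating and Visit 8, and a missing share q of 10% to 20%.
- *Worst earlier ratings are lost.* Bias of the observed mean = −ρ × SD × φ(z₁₋q)/(1 − q). Smallest: 0.3 × 0.75 × 0.1755/0.9 = 0.044. Largest: 0.6 × 0.75 × 0.2800/0.8 = 0.157. Both make the result look better. In simulation the mixed-model mean is nearly unbiased.
- *Worst Visit 8 ratings are themselves lost.* Set ρ = 1 in the formula: 0.146 to 0.262 for the observed mean. The mixed model still carries about 0.10 to 0.25.

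The model's advantage depends on which mechanism holds and on CGAIS being rated before Visit 8. Section 2.9 requires physician questionnaires only at follow-up visits.

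**The case against.** **A one-group route already exists.** This stands, and it limits the point. A reader might infer that the plan has no usable efficacy test, or that only the 80% branch is left for secondary objectives. The documents do not support either. The test against 4 fixes the null value, 2.16.5 fixes Visit 8, and the paired t-test carries over to secondary variables. For scale-graded variables, what is missing is the level and, for the paired test, the baseline value.

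**The deciding test is not wide open.** A reader might infer that it would be picked after the data are seen. That goes too far: the two one-group tests coincide once baseline is 4, and two-sided 0.05 is the only level used anywhere. What remains open is the attachment of that level, the baseline statement and the model details.

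**The analysis sets are not empty in practice.** Taken alone, the randomisation condition would exclude all 120 patients. But 2.16.3 also counts everyone who starts treatment, so this is an internal contradiction with an evident resolution.

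**Treatment groups could mean conditions or body areas.** Nothing in the plan says so, and patients are not randomised to them.

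**It is a feasibility study.** Section 2.1 says so, and the success rule does not use the comparison. That lowers the stakes, but a plan that sets p-value rules should set ones that can be carried out.

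**Conclusion.** The point holds as a structural defect. Both efficacy significance rules in 2.16.5, and the one in 2.16.4, refer to a comparison that one cohort cannot supply. The two one-group tests in the plan have no stated level. The conclusion rests on reading the study as one group. The documents never use the term single-arm, but they define no second group, comparator or allocation.

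A reader might also infer that the study's success decision fails. It does not: the 80% satisfaction rule and the side effect condition stand without the group comparison. No numerical error is claimed, and the figures in Steps 5 and 6 are illustrations on stated assumptions. They support reporting the interval with the p-value, and they do not establish that a mixed model is required.

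**What to change.** - **2.16.3:** delete the randomisation condition. Demographic, medical history and efficacy analyses then include all patients with at least one treatment; safety analyses include those who also have some safety data.
- **2.16.4:** delete the group comparisons and their p-value rule.
- **2.16.5, primary:** define the variable as the CGAIS rating at Visit 8. Replace the pairwise comparison and the paired t-test with a one-sample test of the Visit 8 mean against 4, as in 2.16.1, at two-sided 0.05. Report the mean, its 95% confidence interval and the number of treated patients with no Visit 8 CGAIS.
- **Mixed model:** if the sponsor keeps it for the Visit 8 mean, name the visits at which CGAIS is rated and the covariance structure. Its gain depends on CGAIS ratings before Visit 8 and on dropout being explained by observed ratings.
- **2.16.5, secondary:** for variables graded on a scale with a no-change value, use the same test and level. For others, delete the group-comparison rule and apply the 2.16.1 criterion, with a reference value if significance is used.
- **2.16.5 and 2.16.6:** summarise all treated patients instead of each treatment group.
- **Photograph evaluation:** Section 1.2 lists it under primary objectives, while 2.16.5 bases secondary variables on image grading. Reconcile the two.

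The 2.16.1 success rule stays as it is. The cost is a text amendment with written IRB approval (Section 21.0), recording what interim data had been seen when the test was restated. It needs no new data, visits or patients.
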